### 6.2. DESCRIPTION OF STATISTICAL ANALYSES

### Significance Levels

The Type I error rate for the primary study analysis will be 0.05.

Comparisons for secondary, exploratory, and safety analyses will use  $\alpha$  = 0.05, with no adjustment for multiple comparisons.

#### **Models for Continuous Measures**

Comparisons of study groups with regard to continuous baseline and secondary outcomes will be performed using standard statistical tests and will be chosen as appropriate for the scale and distribution of the measures being analyzed. For example, a t-test, Wilcoxon test, or one-way ANOVA (as appropriate) can be performed to assess differences.

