## Secondary Endpoints:

- Postoperative restoration of femoral offset and leg length
- Radiographic measurements of stability and fixation
- Overall Survivorship
- Harris Hip Score
- Complications

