#### 2.6. ASSESSMENT PROCEDURE

### 2.6.1. ASSESSMENT TIMELINES/SCHEDULE

	Pre-op	Intraop	Immediate Post-op	6 weeks	6 months	1 year	2 years	5 years
Operative Form		Х						
Standard Radiographs	Х			Х		Х	Х	Х
DEXA			Х			Х	Х	Х
Modified Harris Hip Score	Х				Х	Х	Х	Х
Thigh pain	Х			Х	Х	Х	Х	Х
Complications		Any Time						

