#### 6. DATA ANALYSES

#### 6.1. SAMPLE SIZE JUSTIFICATION

We performed a sample size calculation based on detecting a difference in the incidence of postoperative thigh pain between the 2 study groups, assuming an overall  $\alpha$  error (2 sided) of 5% with a statistical power of 80% ( $\beta$  error = .20). We assumed that the incidence of thigh pain in the conventional femoral implant group would be 15% compared to 5% in the short anatomical femoral implant group at 2-year follow-up. With these assumptions, approximately 40 patients per study group were needed.

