#### **Exploratory Analyses**

Exploratory Analyses described below will be carried out if possible, depending on the data. If empty cells exist or models do not converge, these analyses will not be performed.

Repeated measures ANOVA models will be developed for each of the Gruen Zones to determine the effect of visit (time), treatment and baseline value of BMD on the BMD results. Baseline factors may also be included. To determine whether a factor has an effect on the BMD results, a Type 3 analysis of effects based on the F test will be conducted. Hypothesis testing will use  $\alpha$  = 0.05.

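### No baseline-adjusted analysis is planned for the modified Harris Hip Score, although the pre-op score is collected; ANCOVA would be a free gain in precision

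*Combined protocol and SAP*

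**What the plan says.** Section 2.5 lists the "Harris Hip Score" among the secondary endpoints. It does not say whether the post-op score or the change from pre-op is compared, or at which visit. Section 1.4 makes the comparison of clinical scores between the two stems one of the main objectives.

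The assessment schedule in 2.6.1 has a row for the "Modified Harris Hip Score", marked pre-op and at 6 months, 1 year, 2 years and 5 years.

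The analysis rule is in 6.2, under Models for Continuous Measures: "Comparisons of study groups with regard to continuous baseline and secondary outcomes will be performed using standard statistical tests", chosen by the scale and distribution of the measure. It continues, expressly by way of example: "a t-test, Wilcoxon test, or one-way ANOVA (as appropriate) can be performed to assess differences".

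Baseline enters as a model term in one place only. The Exploratory Analyses part of 6.2 plans repeated measures models for each Gruen zone "to determine the effect of visit (time), treatment and baseline value of BMD on the BMD results". There is no counterpart for the Harris score. Under Significance Levels, secondary comparisons are tested at 0.05 without adjustment for multiplicity.

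**The concern.** The pre-op score is a baseline measure of the same quantity as the outcome, so it is usually the first candidate for a covariate. It is already scheduled, but the plan gives it no stated role in the comparison of stems. Choosing a test by scale and distribution does not lead an analyst to adjust for baseline, and none of the three examples does so.

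Two things are at stake, both within a secondary result. One is precision: any variance in the post-op score that the pre-op score explains stays in the error term. The other is chance imbalance: a pre-op difference between arms carries into the unadjusted post-op difference in proportion to r. The open choice of outcome form and visit adds to this, because one of the permitted forms, the change score, can be less precise than ignoring the pre-op score altogether.

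**Working it through.** **Plan's own figure.** There is none for this endpoint. The sample size calculation in 6.1 concerns thigh pain only and is not used here.

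**Inputs from the documents**
- 50 patients per arm (Study Summary).
- Alpha 0.05 for secondary comparisons (6.2). I take it as two-sided, as in 6.1.
- Pre-op and post-op scores both collected (2.6.1).

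**Assumed inputs (not in the documents)**
- Pre/post correlation r within arm: 0 to 0.6.
- True difference between arms: 0.5 SD of the post-op score.
- Equal SDs pre-op and post-op, needed only for the change-score figures.

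**Formulas** (variance relative to a t-test on the post-op score)
- ANCOVA: 1 − r². Effective effect size 0.5/√(1 − r²).
- t-test on change: 2(1 − r). Effective effect size 0.5/√(2(1 − r)).
- Change against ANCOVA: 2(1 − r)/(1 − r²) = 2/(1 + r).

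Power is from the two-sample t-test (noncentral t) at these effect sizes. Example at r = 0.5: ANCOVA variance 1 − 0.25 = 0.75, effect size 0.5/√0.75 = 0.577, power 82%. The change-score variance is 2 × 0.5 = 1.00, so the effect size stays at 0.5 and power at 70%.

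**Results at 50 per arm.** The t-test on the post-op score has 70% power throughout.

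| r | ANCOVA variance | Cut | ANCOVA power | Change-score variance | Change-score power | Change / ANCOVA variance |
|---|---|---|---|---|---|---|
| 0 | 1.00 | 0% | 70% | 2.00 | 42% | 2.00 |
| 0.2 | 0.96 | 4% | 71% | 1.60 | 50% | 1.67 |
| 0.3 | 0.91 | 9% | 74% | 1.40 | 55% | 1.54 |
| 0.5 | 0.75 | 25% | 82% | 1.00 | 70% | 1.33 |
| 0.6 | 0.64 | 36% | 87% | 0.80 | 79% | 1.25 |

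At r = 0.5, ANCOVA on 50 per arm is worth 50/0.75 ≈ 67 per arm unadjusted.

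**Fewer patients.** With 40 per arm analysed, the post-op t-test has 60% power. ANCOVA gives 64% / 72% / 79% at r = 0.3 / 0.5 / 0.6.

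**Cost of the covariate.** Fitting it inflates the variance by about 1/(2 × 50 − 4) = 1/96, or 1%. ANCOVA is therefore ahead once (1 − r²)(1 + 1/96) < 1, that is r² > 1/97, or r above about 0.10.

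**Chance imbalance.** The standard error of the pre-op difference between arms is √(2/50) = 0.2 SD. At r = 0.5, an imbalance of one standard error moves the unadjusted post-op difference by 0.5 × 0.2 = 0.1 SD. ANCOVA removes that shift.

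**The case against.** Three stronger readings are tempting, and the documents do not support them.

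- A reader might infer that the plan prescribes an unadjusted test. It does not. The three tests are introduced as examples that can be performed, and ANCOVA is neither named nor excluded. What stands is that no adjusted analysis is specified.
- A reader might infer that the named tests cannot use the pre-op score. Each can be run on change from pre-op, and the plan does not rule that out. What stands is that change is the less efficient use: its variance is 2/(1 + r) times that of ANCOVA, and for r below 0.5 it is less precise than the post-op score alone.
- A reader might infer that an unadjusted comparison is biased. Under randomisation it is valid, and its standard error already covers chance imbalance. The loss is one of precision.

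The remaining objections concern size. Neither r nor the 0.5 SD difference is in the documents, and at r of 0.2 or less the gain is negligible. The endpoint is secondary and the trial was not sized for it. A repeated measures model with baseline, like the one planned for BMD, would serve as well as ANCOVA by visit. All of this is fair, and it limits the point to a minor one. It does not remove it: at r = 0 the change costs about one degree of freedom, and at moderate r it gains materially with no new data.

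**Conclusion.** The point holds as a free improvement of minor severity. For the modified Harris Hip Score the plan names only tests without a covariate and plans no baseline-adjusted analysis, although the pre-op score will be on file for this purpose.

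The gain rests wholly on r. It is nil at r = 0, small up to about 0.3 (power 70% to 74% for 0.5 SD at 50 per arm), and material at 0.5 to 0.6 (82% to 87%). The power figures also depend on the assumed 0.5 SD difference, and the change-score figures on equal SDs before and after surgery. The validity of the secondary comparison and the primary conclusion are not affected.

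**What to change.** Add one sentence to Models for Continuous Measures in 6.2: the modified Harris Hip Score will be compared by ANCOVA of the post-op score on assigned arm and pre-op score, with 2 years as the lead visit and the other visits supportive, reporting the adjusted mean difference with its 95% confidence interval. Two years is also the time point of the thigh pain assumption in 6.1.

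A rank-based analysis may be named as a sensitivity analysis if residuals are clearly skewed. A site term, or one repeated measures model with the pre-op score as covariate in place of visit-by-visit ANCOVA, is optional.

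The cost is one SAP sentence and about one degree of freedom. No extra data, visits or patients are needed.

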#### **Categorical Data Analyses**

Comparisons of study groups with regard to categorical baseline, secondary and safety outcomes will be performed using standard statistical tests and will be chosen as appropriate for the scale and distribution of the measures being analyzed.

#### **Exploratory Analyses**

Exploratory Analyses described below will be carried out if possible, depending on the data. If empty cells exist or models do not converge, these analyses will not be performed.

Repeated measures ANOVA models will be developed for each of the Gruen Zones to determine the effect of visit (time), treatment and baseline value of BMD on the BMD results. Baseline factors may also be included. To determine whether a factor has an effect on the BMD results, a Type 3 analysis of effects based on the F test will be conducted. Hypothesis testing will use  $\alpha$  = 0.05.

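### BMD change is a primary endpoint, but section 6.2 gives it no primary analysis: its only model is exploratory, unadjusted across Gruen zones, and has no primary zone, primary visit or fallback

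*Combined protocol and SAP*

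**What the plan says.** **Status of BMD.** The Study Summary gives BMD change as the primary purpose and, across the Gruen zones, as a primary outcome. Section 1.1 makes it the primary aim, section 2.5 lists it first of two primary endpoints, and it is the only subject of the hypothesis in section 2.4.

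**Error rate.** Section 6.2, Significance Levels: "The Type I error rate for the primary study analysis will be 0.05". No paragraph says what that primary analysis is. Secondary, exploratory and safety comparisons are each made at 0.05, "with no adjustment for multiple comparisons".

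**Named tests.** Models for Continuous Measures: "Comparisons of study groups with regard to continuous baseline and secondary outcomes will be performed using standard statistical tests". Categorical Data Analyses: "Comparisons of study groups with regard to categorical baseline, secondary and safety outcomes will be performed using standard statistical tests". Neither paragraph includes primary outcomes.

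**The BMD model.** It appears only under Exploratory Analyses: "Repeated measures ANOVA models will be developed for each of the Gruen Zones", with visit, treatment and baseline BMD as effects and F tests at 0.05. Two conditions are attached: "Exploratory Analyses described below will be carried out if possible, depending on the data" and "If empty cells exist or models do not converge, these analyses will not be performed". Covariates are open: "Baseline factors may also be included".

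**Visits.** The schedule in section 2.6.1 has DEXA immediately after surgery and at 1, 2 and 5 years. None is marked as the primary time point.

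**The concern.** A primary endpoint needs one analysis, fixed in advance, whose result decides the question at the stated error rate. For BMD the plan supplies only a set of models that it classes as exploratory, and it allows them to be omitted depending on the data.

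Two consequences follow. Taken literally, the trial's leading endpoint has no confirmatory test, and the 0.05 set for the primary analysis attaches to nothing defined for BMD. If the zone models are instead treated as the primary test, several tests are made at 0.05 each and the overall false-positive chance is higher than the plan states. Either way, the plan does not say which zone and visit decides the endpoint, so that would be settled with the results in view.

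**Working it through.** **Step 1. Does any paragraph of section 6.2 supply a primary BMD analysis?**

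| Paragraph | Outcomes covered | Primary BMD analysis? |
|---|---|---|
| Significance Levels | Sets 0.05 for a primary analysis | No: the analysis is not defined |
| Models for Continuous Measures | Baseline, secondary | No |
| Categorical Data Analyses | Baseline, secondary, safety | No |
| Exploratory Analyses | BMD in each Gruen zone | Names BMD, but as exploratory, conditional and unadjusted |

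None does. Section 6.2 reads as continuous text, with no sign that a redaction or a lost table explains the gap.

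**Step 2. False-positive chance if the zone models are read as the primary test.**

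Input from the plan: 0.05 per zone, no adjustment. The plan gives neither the number of zones, K, nor their correlation, r. Both are assumed: K = 3 to 7, and r = 0 or 0.5 to 0.8.

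For independent zones, the chance of at least one false positive is 1 − 0.95^K. For correlated zones it was simulated with 1,000,000 draws of K equally correlated standard normal statistics, counting draws in which any exceeded 1.96 in absolute value.

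| K (assumed) | Independent | r = 0.5 | r = 0.8 |
|---|---|---|---|
| 3 | 1 − 0.95^3 = 0.143 | 0.126 | 0.098 |
| 5 | 1 − 0.95^5 = 0.226 | 0.183 | 0.127 |
| 7 | 1 − 0.95^7 = 0.302 | 0.230 | 0.148 |

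So it is 14% to 30% if independent, and about 10% to 23% at r of 0.5 to 0.8. These figures count one treatment test per zone.

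**Step 3. The drop rule.**

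The rule has two triggers, empty cells and non-convergence. The plan does not define an empty cell, name the optional baseline factors or give a covariance structure, so the chance of triggering it cannot be computed. With about 50 patients per arm, an empty arm-by-visit cell is remote. What the text does establish is that no other analysis is named if the rule is triggered.

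**Step 4. What a single primary contrast could detect.**

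The plan has no BMD effect size, standard deviation (SD) or power figure to reproduce; section 6.1 is based on thigh pain alone. The calculation is a two-sample t-test on change, two-sided, 80% power, in units of the SD of change. It uses 50 per group (Study Summary) and 40 per group (the number in section 6.1, taken here only as a possible evaluable number). The normal approximation is (z for alpha + z for power) × √(2/n). For one contrast this is (1.960 + 0.842) × √(2/50) = 0.56; the t-test values below are slightly larger.

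| Test | Alpha | 50 per group | 40 per group |
|---|---|---|---|
| One named contrast | 0.05 | 0.566 | 0.634 |
| First Holm step, 3 zones (assumed) | 0.05/3 = 0.0167 | 0.657 | 0.737 |
| First Holm step, 7 zones (assumed) | 0.05/7 = 0.0071 | 0.720 | 0.809 |

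A baseline-adjusted model is generally at least as precise as an unadjusted t-test, so these values are likely conservative for the model proposed below.

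**The case against.** **The general test paragraph could serve.** It offers a t-test, Wilcoxon test or one-way ANOVA as examples for continuous measures. But its own wording confines it to baseline and secondary outcomes. Stretching it to BMD would still leave the test, zone and visit open.

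**The plan breaks no promise on error rates.** It openly declines adjustment for exploratory analyses, and the zone models carry that label. This stands: read as labelled, they breach nothing. The inflation in Step 2 applies only if they are used as the primary test. But if they are not, the primary endpoint has no test.

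**Nothing is selected.** A reader might infer that the analyst would choose which zone to analyse. The text does not support that: a model is planned for every zone, with visit in it. What is open is which of those results counts as primary.

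**The drop rule will rarely apply.** This probably stands. A reader might add a sparse diagnosis category as an optional baseline factor and compute how often it would occur in one arm only. That is not the chance of losing the BMD analysis: a main-effect category seen in one arm still leaves the treatment effect estimable, and an optional covariate can be left out.

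**Dilution and similarity.** A reader might also infer that the treatment effect will be averaged over visits, or that a non-significant result will be reported as similarity. The plan does not rule out a treatment-by-visit term, and nowhere says a null result will be reported that way. Neither inference is part of this point.

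**Conclusion.** The point holds and should be corrected. That BMD has no primary analysis follows from the text alone and needs no assumption.

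The size of the multiplicity problem, roughly 10% to 30% against the stated 0.05, is conditional. It assumes 3 to 7 zones, correlation from none to 0.8, and that the zone models are taken as the confirmatory test. The direction holds for any number of zones above one unless their results are perfectly correlated.

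It would go too far to say that the BMD analysis is likely to be dropped, since the documents give no basis for a probability. The objection to the drop rule is one of principle: a data-dependent omission without a fallback should not apply to a primary endpoint.

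Three neighbouring matters need separate treatment and are not counted here: thigh pain is a secondary aim in section 1.1 but primary in the Study Summary and section 2.5; no sharing of alpha between the two primary endpoints is stated; and sections 2.4 and 1.3 leave it unclear whether a null hypothesis or a similarity claim is meant.

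**What to change.** In section 6.2:

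1. Move the existing repeated-measures model (BMD on baseline BMD, visit and treatment) into a primary-analysis paragraph and add a treatment-by-visit term.
2. Before BMD results by group are seen, name one primary visit and one primary zone or defined composite, or apply Holm across zones. The choice is the sponsor's.
3. Report that treatment difference with a 95% confidence interval, and label other zones and visits secondary.
4. For BMD, replace the rule that the analysis is omitted with an ordered fallback, for example a simpler covariance structure, then ANCOVA on baseline BMD at the primary visit.

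**Cost.** SAP wording and modest programming; no new patients, visits or scans. One named contrast tested at the full 0.05 can detect about 0.57 SD of change with 50 per group (0.63 with 40). Holm raises the first-step figure to 0.66 (0.74) for an assumed 3 zones and 0.72 (0.81) for 7, so naming one zone or composite avoids that loss. If BMD later has to share alpha with thigh pain, the detectable difference should be recalculated.

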#### 7. DATA COLLECTION, HANDLING AND RETENTION

#### 7.1. SOURCE DOCUMENT REQUIREMENTS

Source documentation for this study will be maintained to document the treatment and study course of a subject and to substantiate the integrity of the study data. Source documentation may include, but not be limited to, worksheets, hospital and/or clinic or office records documenting subject visits including study and other treatments or procedures, medical history and physical examination information, laboratory and special assessments results, pharmacy records, device accountability records, and medical consultations (as applicable).

Before the study starts, a record of the source document for each endpoint will be recorded and kept at the site and with the Sponsor. If for any reason this source document changes, the record will need updated, and communicated to the Sponsor.

#### 7.2. CASE REPORT FORMS

Data for this study will be collected and documented on the subject Case Report Forms (CRFs) provided which may be in paper form or in an electronic form. Authorized study site personnel will complete CRFs only. CRFs must be reviewed for completeness and accuracy, and signed by the investigator or his/her designees.

Since there is a potential for errors, inaccuracies, and misinterpretation in transcribing data onto the CRFs, the following documents must be available at all times for inspection and comparison to the CRFs by the study monitor when appropriate:

- data query forms
- originals and photocopies/certified copies of all relevant records and reports
- copies of test results

Sample CRFs to be used with this study are provided in Appendix 2.

#### 7.3. ELECTRONIC DATA ENTRY

When using electronic data handling and/or remote electronic data systems, the Sponsor should:

- Ensure and document that the electronic data processing system(s) conforms to the Sponsor's established requirements for completeness, accuracy, reliability, and consistent intended performance (i.e. validation).
- Maintain SOPs for using these systems.
- Ensure that the systems are designed to permit data changes in such a way that the data changes are documented and that there is no deletion of entered data (i.e. maintain an audit trail, data trail, edit trail).
- Maintain a security system that prevents unauthorized access to the data.
- Maintain a list of the individuals who are authorized to make data changes.
- Maintain adequate backup of the data.
- Safeguard the blinding, if any (e.g. maintain the blinding during data entry and processing).

#### 7.4. STUDY DOCUMENT RETENTION

Study documents should be retained for a season after the study is complete as required by local, state, national, or international health authorities.

#### 8. DATA REPORTING

The site will provide study progress and data summary reports to the Sponsor per frequency agreed by both parties.

### 9. MONITORING PLAN

The Sponsor of this study may monitor the data collection to ensure that the study is being conducted consistent with the protocol. The following describes the monitoring activities, which may take place during the course of the study.

#### 9.1. FREQUENCY

### **Pre-Study Visit/Conference:**

Prior to initiation of the study, the study manager will provide the investigator with all the necessary information to enable him/her to carry out his/her responsibilities. This prepares the site with an in-depth training on the protocol, CRFs, and data collection process for the length of the study. The study manager will also train the site on using the Sponsor's Joint Assist database.

# **Monitoring of the Data**

Monitoring of the data will occur at least annually, and as often as monthly. Times when this may be appropriate include:

- Monthly Invoicing
- Quarterly Review
- Annual Reports
- While performing data analysis for marketing material or publication.

#### 9.2. SAMPLING PLAN

All data will be monitored for completeness and accuracy on at least an annual basis.

